3.2. Statistical Hypothesis

The study is designed to test the hypothesis whether patients treated with BIVV009 will achieve a response rate greater than 30%. Statistical hypothesis is written as

$$H_0: \text{response rate} \leq 30\%$$

$$H_1: \text{response rate} > 30\%,$$

where the response rate is the proportion of patients in the intent-to-treat (ITT) population who meet the response criteria defined in Table 2 of the protocol.

Based on discussions with key opinion leaders and experienced clinicians, a response rate of less than 30% is not considered clinically relevant. It is expected that few patients with transfusion dependent primary CAD would meet the responder definition for the primary endpoint without treatment intervention, and as such a null hypothesis of $\leq 30\%$ responder rate for this patient population is reasonable.

3.3. Sample Size Justification

Approximately 20 patients with primary CAD who have a recent history of transfusion will be enrolled. If the true responder rate is estimated to be 66% and a minimum of 30% is required for success, then with 20 patients there is 90% probability that the lower limit of the 95% confidence interval (CI) will be at least 30%.

3.4. Randomization and Blinding

This is an open-label study with no blinding or randomization. Despite the nature of the open-label study, the aggregated summary of efficacy endpoints described below will not be shared with the Sponsor study team until the execution of Part A analysis.

3.5. Interim Analysis

For the purposes of regulatory submission, an interim analysis of safety and efficacy data (Part A analysis) will be performed for Part A after all patients have completed Part A and the data are cleaned. Parts A and B will have separate database locks to enable submission of the BLA/MAA following completion of Part A. Additional analyses of Part B data will be defined in a separate Part B SAP.

Since Part A analysis constitutes the primary analysis of the study hypothesis, no Type I error adjustment is necessary.

4. ANALYSIS POPULATIONS

The following analysis populations are defined for Part A of the study. For the remainder of the SAP, the term “subjects” will be used to refer to patients in the study to keep consistent with the term used within table, figure, and listing (TFL) displays.

4.1. Full Analysis Set (FAS)

The ITT population consists of all subjects who received at least 1 dose (including partial dose) of study drug. All subjects in the ITT population will be included in the Full Analysis Set. Analyses of efficacy will be performed on the FAS. For analysis, FAS and the ITT population are considered exchangeable in the SAP, but the term FAS will be used in subsequent sections of the SAP and TFLs.

4.2. Per-protocol Set

The per-protocol (PP) population is defined as a subset of FAS who do not have any important protocol deviations impacting their efficacy assessments (defined in [Section 6.3](#)). Selected efficacy endpoints will be analyzed for the PP Population.

4.3. Safety Analysis Set

Subjects who received at least 1 dose (including partial dose) of study drug will be included in the Safety Analysis Set. Note that Safety Analysis Set is the same as FAS in this study.

4.4. PK Analysis Set

Subjects who received at least 1 dose of study drug and have evaluable PK concentrations will be included in PK analysis set.

4.5. PD Analysis Set

All subjects who receive at least 1 dose of study drug and have at least 1 evaluable PD sample during Part A will be included in the PD analysis population.

4.6. Definitions of Subgroups

The following subgroups will be considered for the selected analyses:

- Age ($< 65, \geq 65$)
- Gender (Female, Male)
- Baseline weight ($< 75 \text{ kg}, \geq 75 \text{ kg}$)
- Number of transfusions within 12 months prior to study entry ($\leq 2, > 2 -4, > 4$)
- Baseline Hgb level ($< 8.5 \text{ g/dL}, \geq 8.5 \text{ g/dL}$)

- Previous rituximab therapy and/or cytotoxic therapy (Yes, No)

In case of very few subjects (e.g., < 5) in a category, the cutoff value may be changed to suit the distribution of these factors.

5. DEFINITIONS AND DATA HANDLING

Statistical analysis will be performed by Bioverativ, using SAS[®] version 9.3 or higher and, where appropriate, additional validated software. This SAP is based on protocol Version 5, dated 17 July 2018.

5.1. General Principles

Safety, efficacy, and PK/PD data will be summarized using standard summary statistics for continuous, categorical, and event time data. Data will be summarized for the populations defined. All statistical hypothesis testing will be performed at the 2-sided, 5% significance level, unless otherwise specified. All p-values will be presented to 3 decimal places; p-values less than 0.001 will be presented as “< 0.001”, and p-values greater than 0.999 will be presented as “> 0.999”. All baseline, efficacy, and safety data, including derived variables at all visits, will be listed.

5.1.1. Definitions

Study Day

Study Day is defined as days relative to the date of first dose of BIVV009, Day 0. In other words, Study Day 1 is Day 0 as defined in the protocol. The start/stop day of events will be calculated as (date of event – date of Study Day 1 + 1) if the date of event is on or after the first dose date, or (date of event – date of Study Day 1) if the date of event is before the first dose date.

Incomplete dates will be imputed for the calculation of study days, unless specified otherwise:

- If missing day only, the start date will be imputed as the first day of the month, while the end date will be imputed as the last day of the month;
- If missing day and month, the start date will be imputed as the first day of the year, while the end date will be imputed as the last day of the year;

Baseline

Baseline measures are defined as the last value prior to the administration of the study drug. If a transfusion occurs during the screening period, the baseline measure must be at least 7 days after the transfusion.

Part A Study Treatment Period

The Part A study treatment period starts at the date of first study drug administration and ends at the date of Week 26 visit if the subject completes Part A study treatment, or at the date of Early Termination (ET)/Safety Follow-up Visit if the subject discontinues the study treatment prior to Week 25.

Visit Windows

Analysis by study visit will utilize the data recorded on the corresponding nominal visit from electronic Case Report Forms (eCRFs). In case of missing data/assessments for a visit, data from an unscheduled visit, or EOT/ET/Safety Follow-up Visit will be used, if the Study Day of such a visit fits in the analytic window defined in [Table 1](#). If multiple values are identified within the analytic window, the one closest to the target study day will be used.

Table 1: Analytic Visit Windows

Visit	Target Study Day	Analytic Visit Window (Study Day)
Baseline (Day 0)	1	≤ 1
Week 1 (Day 7)	8	2 – 15
Week 3 (Day 21)	22	16 – 29
Week 5 (Day 35)	36	30 – 43
Week 7 (Day 49)	50	44 – 57
Week 9 (Day 63)	64	58 – 71
Week 11 (Day 77)	78	72 – 85
Week 13 (Day 91)	92	86 – 99
Week 15 (Day 105)	106	100 – 113
Week 17 (Day 119)	120	114 – 127
Week 19 (Day 133)	134	128 – 141
Week 21 (Day 147)	148	142 – 155
Week 23 (Day 161)	162	156 – 169
Week 25 (Day 175)	176	170 – 179
Week 26 (Day 182; EOT Visit in Part A)	183	180 – 189

Treatment Assessment Timepoint

The value of an assessment (e.g., Hgb) at the treatment assessment timepoint is defined as the average of the values from Week 23, 25, and 26 visits. In the case of any missing value at any of these visits, it will be calculated as the average of the available values, unless no value is available from all three visits.

Solicited Symptomatic Anemia

The severity of CAD symptomatic anemia is defined in [Table 2](#). The severity grading for symptomatic anemia was adopted based on Common Toxicity Criteria for Adverse Events (CTCAE) grades and is collected in eCRFs at every visit.

Table 2: Severity Grade for Symptomatic Anemia Related CAD

CAD Symptomatic Anemia Term	Grade 1	Grade 2	Grade 3	Grade 4
Fatigue	Fatigue relieved by rest	Fatigue not relieved by rest; limiting instrumental ADL	Fatigue not relieved by rest, limiting self-care ADL	Not defined
Weakness	Uneasiness or lack of well being	Uneasiness or lack of wellbeing; limiting instrumental ADL	Not defined	Not defined
Shortness of Breath	Shortness of breath with moderate exertion	Shortness of breath with minimal exertion; limiting instrumental ADL	Shortness of breath at rest; limiting self-care ADL	Life-threatening consequences; urgent intervention indicated
Palpitations, fast heart beat	Mild symptoms; intervention not indicated	Intervention indicated	Not defined	Not defined
Lightheadedness	Not defined	Present (e.g., near fainting)	Not defined	Not defined
Chest Pain	Mild pain	Moderate pain; limiting instrumental ADL	Pain at rest; limiting self-care ADL	Not defined

ADL = activities of daily living

Thromboembolic Events

The thromboembolic events prior to study entry are recorded as medical history in the eCRFs, while thromboembolic events on study are captured as adverse events. Both medical history and adverse events will be coded according to Medical Dictionary for Regulatory Activities (MedDRA) v20.1 or higher.

In general, thromboembolic events may include but are not limited to:

- Any venous events
 - Portal vein obstruction
 - Deep vein thrombosis
 - Pulmonary embolism
 - Mesenteric (abdominal) venous thrombosis

- Any cerebral events
 - Cerebral infarction, occlusion, and stenosis of cerebral and precerebral arteries
 - Vascular syndromes of brain in cerebrovascular diseases, transient cerebral ischemic attacks, and related syndromes
- Any arterial events
 - Myocardial infarction
 - Mesenteric arterial thrombosis
 - Other arterial embolism and thrombosis

Medical review of medical history and AEs will ascertain thromboembolic events for analysis.

Normalization of Bilirubin

The normalization of bilirubin is defined as total bilirubin \leq upper limit of normal (ULN) (specified by the central lab).

Normalization of LDH

The normalization of LDH is defined as LDH value \leq ULN (specified by the central lab).

Normalization of Haptoglobin

The normalization of haptoglobin is defined as haptoglobin above the level of detection.

Hemolytic Breakthrough

Hemolytic breakthrough at any visit is defined as

- A decrease of 2 g/dL or more in Hgb from the last scheduled visit, and
- One of the followings:
 - An increase in LDH from the last scheduled visit,
 - An increase in bilirubin from the last scheduled visit, or
 - A decrease in haptoglobin from the last scheduled visit.

Protocol Prohibited CAD Medications

The following concomitant medications are prohibited during the study treatment period in Part A:

- Rituximab alone or as part of combination therapy
- Cytotoxic drugs (such as fludarabine, bendamustine, ibrutinib, cyclophosphamide)
- Other investigational drug

The efficacy endpoint (estimand) accounting for protocol prohibited CAD medication use will be based on the eCRF questionnaire “Did the subject receive any prohibited medications since the last visit?” at post-baseline visits. The medical review for the list of prohibited medications will be reconciled with the eCRF questionnaire.

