2.2.3. Exploratory Endpoints

Part A:

- Time to first transfusion after the first 5 weeks of study drug administration
- Mean change from baseline in QOL, as assessed by the change in the five level EuroQol – five dimensions questionnaire (EQ-5D-5L) scores at the treatment assessment endpoint
- Mean change from baseline in QOL, as assessed by the change in the 12-item short form survey (SF-12[®]) at the end of treatment assessment endpoint
- Incidence of solicited symptomatic anemia at EOT
- Proportion of patients with Hgb level of ≥ 12 g/dL at the treatment assessment endpoint
- Incidence of thromboembolic events after the first 5 weeks of study drug administration
- Median time to normalization of bilirubin
- Median time to normalization of LDH
- Median time to normalization of haptoglobin
- Median time to obtain Hgb level of ≥ 12 g/dL
- Proportion of patients normalizing haptoglobin at the treatment assessment endpoint
- Proportion of patients normalizing bilirubin at the treatment assessment endpoint

- Proportion of patients normalizing LDH at the treatment assessment endpoint
- Patient's Global Impression of Change (PGIC) to assess patient's perception of changes in CAD disease burden at EOT
- Patient's Global Impression of [Fatigue] Severity (PGIS) to assess the patient's perception of changes in fatigue at EOT
- Incidence of disabling circulatory symptoms at EOT
- Total healthcare resource utilization at EOT

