7.2.2. Sensitivity Analyses

Sensitivity analyses will be carried out based on the completer estimand and the per-protocol estimand (defined in [Table 3](#)). The proportion of subjects with treatment response will be summarized along with the 95% exact Clopper-Pearson CI.

Table 3: Estimands for Primary Endpoint

	Composite Estimand	Completer Estimand	Per-protocol Estimand
Population	FAS	A subset of FAS with those who complete treatment at least through Week 23 and have at least 1 evaluable Hgb from Week 23, 25, and 26	A subset of FAS with those who are free of important protocol deviations defined in Section 6.3
Response Variable	Responder if 
 Free of post-baseline transfusion within the range of Week 5 and Week 26 visit dates, and Hgb at treatment assessment timepoint ≥ 12 g/dL, or the change from baseline at treatment assessment ≥ 2 g/dL, and Receive no protocol prohibited medications defined in Section 5.1.1 within the range of Week 5 and Week 26 visit dates, and Remain in study through at least Week 23, and At least 1 evaluable Hgb from Weeks 23, 25, and 26 	Responder if 
 Free of post-baseline transfusion within the range of Week 5 and Week 26 visit dates, and Hgb at treatment assessment timepoint ≥ 12 g/dL, or the change from baseline at treatment assessment ≥ 2 g/dL, and Receive no protocol prohibited medications defined in Section 5.1.1 within the range of Week 5 and Week 26 visit dates 	Responder if 
 Free of post-baseline transfusion within the range of Week 5 and Week 26 visit dates, and Hgb at treatment assessment timepoint ≥ 12 g/dL, or the change from baseline at treatment assessment ≥ 2 g/dL
Treatment effect	Proportion of subjects who achieve the composite response variable (defined above)	Proportion of subjects who achieve the treatment response	Proportion of subjects who achieve the treatment response

In the case when there are at least 2 subjects who discontinue study participation prior to Week 5, a supportive analysis, similar to the primary analysis, will be performed by excluding those subjects who discontinue prior to Week 5.

In the case of normal ranges (LLN) varying across local labs, a sensitivity analysis will be performed for the primary endpoint by qualifying normalization of Hgb using \geq LLN, instead of ≥ 12 g/dL.

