Part A: Plot of mean change from baseline in bilirubin (umol/L) (+/- SE) by visit (excluding subjects with Gilbert's syndrome) - Observed
Part A: Plot of mean lactate dehydrogenase (U/L) (+/- SE) by visit - Observed
Part A: Plot of mean change from baseline in lactate dehydrogenase (U/L) (+/- SE) by visit - Observed
Part A: Plot of mean haptoglobin (g/L) (+/- SE) by visit - Observed
Part A: Plot of mean change from baseline in haptoglobin (g/L) (+/- SE) by visit - Observed
Part A: Plot of mean absolute reticulocyte ($10^9/L$) (+/- SE) by visit - Observed
Part A: Plot of mean change from baseline in absolute reticulocyte ($10^9/L$) (+/- SE) by visit - Observed
Part A: Summary of proportion of subjects normalizing hemolytic parameters at the treatment assessment timepoint - Observed
Part A: Summary of time to first normalization of hemolytic parameters (1) - Observed
Part A: Summary of time to first normalization of hemolytic parameters (2) - Observed
Part A: Plot of hemoglobin (g/dL) by visit by response - Observed
Part A: Summary of shift to non-detectable/detectable in haptoglobin by visit - Observed
Efficacy: Exploratory - CAD Events
Part A: Summary of incidence of solicited symptomatic anemia by visit
Part A: Summary of incidence of solicited symptomatic anemia improvement by visit
Part A: Summary of incidence of other CAD-related symptoms by visit

[figure not shown]
Part A: Summary of incidence of thromboembolic events after the first 5 weeks of BIVV009 administration
Part A: Summary of time to first transfusion after the first 5 weeks of BIVV009 administration
Part A: Plot of time to first transfusion after the first 5 weeks of BIVV009 administration
Part A: Summary of time to first transfusion including the first 5 weeks of BIVV009 administration
Part A: Summary of transfusions by study period
Efficacy: Exploratory - PRO
Part A: Summary of FACIT-Fatigue score and change from baseline by visit
Part A: Plot of mean FACIT-Fatigue score (+/- SE) by visit
Part A: Summary of EQ-5D index score and change from baseline by visit
Part A: Summary of EQ-5D-5L visual analogue scale (VAS) and change from baseline by visit
Part A: Summary of EQ-5D-5L descriptive system
Part A: Summary of SF-12 component scores and change from baseline by visit
Part A: Summary of SF-12 sub-scale scores and change from baseline by visit
Part A: Summary of Patient's Global Impression of Change (PGIC)
Part A: Summary of Patient's Global Impression of Fatigue Severity (PGIS) by visit

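### The Part A SAP counts any detectable haptoglobin as normalised, so its exploratory haptoglobin endpoints do not show how many patients reach the normal range

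*SAP*

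**What the plan says.** The Part A SAP, Section 5.1.1, gives three consecutive definitions of normalisation.

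- Bilirubin: total bilirubin at or below the "upper limit of normal (ULN) (specified by the central lab").
- LDH: "The normalization of LDH is defined as LDH value" at or below the same kind of central-laboratory limit.
- Haptoglobin: "The normalization of haptoglobin is defined as haptoglobin above the level of detection".

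The haptoglobin definition feeds exploratory endpoints only. Section 2.2.3 lists "Proportion of patients normalizing haptoglobin at the treatment assessment endpoint" and "Median time to normalization of haptoglobin". Section 7.4.1.2 adds the proportion by visit, and Section 7.4.1.3 implements the time endpoint as time to the first qualifying value. Protocol Section 4.3.3 lists the two Section 2.2.3 endpoints without defining normalisation. Protocol Section 7 lets the SAP prevail where the two differ, so the SAP definition governs. The SAP gives no reason for choosing detectability.

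The table list in SAP Section 12 also contains a separate output, "Summary of shift to non-detectable/detectable in haptoglobin by visit".

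**The concern.** One word carries two standards. For bilirubin and LDH, a normalised patient is within the laboratory's reference limit. For haptoglobin, a normalised patient may still be below it. Section 12 plans a single summary of the proportion of subjects normalising hemolytic parameters, where a reader would naturally apply one meaning throughout.

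What is at stake is the interpretation of a few exploratory results. The endpoints named in the protocol suggest a return to the normal range; as defined in the SAP, they report a return to measurable levels. The two can coincide, but nothing in the documents shows that they do.

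**Working it through.** The plan gives no haptoglobin figure to reproduce. Its only design figures concern the primary responder rate (Protocol Section 7.10), and haptoglobin does not enter that calculation. The check is therefore a comparison of definitions, followed by what can be said about direction and size.

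**1. Inputs.** Write LOD for the detection limit and LLN for the central laboratory's lower limit of normal. The current criterion is value > LOD (SAP 5.1.1). The criterion parallel to bilirubin and LDH would be value ≥ LLN. Neither LOD nor LLN appears in the protocol or SAP, and neither document contains haptoglobin data.

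**2. Where the criteria differ.** They disagree for values with LOD < value < LLN, which count as normalised now but lie below the normal range. They agree in practice only if LOD is at or above LLN, or if no patient falls in that gap.

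**3. Direction, assuming LOD < LLN.** Every value at or above LLN is also above LOD.

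- Proportions, at the treatment assessment timepoint and by visit, with the same patients in the denominator: the share at or above LLN is at most the share above LOD.
- Time: a patient's first value at or above LLN cannot come before the first value above LOD, so each patient's time stays equal or lengthens. The Kaplan-Meier median will ordinarily move the same way, although censoring between the two times means this is not a strict rule in a small sample.

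**4. Size.** Overstatement of a proportion = k/n, where n is the number of evaluable patients and k the number of those in the gap. If all 20 planned patients were evaluable, each patient in the gap would account for 1/20 = 5 percentage points. The value of k is unknown and can be 0, so the range starts at no overstatement. The value n = 20 is also an assumption: Section 7.4.1 uses the Observed Estimand, which keeps only patients with evaluable values.

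**5. Does another planned output show the LLN count?**

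| Part A SAP output | Haptoglobin against LLN? |
|---|---|
| Chemistry summaries (8.2.1) | No; haptoglobin is not among the listed tests |
| Directional shift summary (8.2.1.2, Table 8) | No; haptoglobin is not in the table |
| Potentially clinically significant abnormalities (8.2.1.3) | No; haptoglobin is explicitly excluded |
| Mean change by visit and plots (7.4.1.1, Section 12) | No; means only, no count |
| Detectable/non-detectable shift (Section 12) | No; detectability only |
| Laboratory listings (8.2) | Abnormal values flagged patient by patient, not summarised |

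No planned summary gives the count.

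**6. A related gap in the same rule.** The treatment assessment value is the mean over Weeks 23, 25 and 26 (5.1.1), and the SAP does not say how a result below LOD enters that mean. Suppose two of the three results are below LOD and each is replaced by s × LOD. The mean exceeds LOD when the third value exceeds (3 − 2s) × LOD: 3 × LOD if s = 0, 2 × LOD if s = 1/2, and LOD itself if s = 1. The same patient can therefore be counted either way under the present wording.

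**The case against.** The strongest reply is that this is a disclosed operational definition of exploratory endpoints. No haptoglobin endpoint is primary or secondary, and Section 7.1.1 tests nothing formally beyond the primary hypothesis. That stands, and it limits the point to labelling and interpretation.

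Nor does the SAP use reference limits throughout. Normalisation of Hgb in Sections 7.4.1.2 and 7.4.1.3 means a fixed 12 g/dL. The LLN enters only through a conditional sensitivity analysis in Section 7.2.2 ("In the case of normal ranges (LLN) varying across local labs"). That also stands: haptoglobin is not the sole exception to a uniform rule. The contrast with bilirubin and LDH remains, and the SAP does not explain it.

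Persistently low haptoglobin would also not be hidden. Means, changes and plots by visit are planned, and in a study of about 20 patients the listings would let a reader count those below the LLN. This reduces the harm, but a hand count from listings is not a planned summary.

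Three stronger readings are tempting and are not supported.

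- A reader might infer that the SAP would declare haemolysis itself normalised. The endpoint concerns one analyte, reported beside separate Hgb, bilirubin, LDH and reticulocyte summaries.
- A reader might infer that patients far below the LLN will be counted, or that the proportion will certainly fall once the definition changes. Both depend on assay limits and data that the documents do not give.
- A reader might infer that the normalisation endpoints merely duplicate the detectability shift table. That table is by visit; it gives neither the time to first normalisation nor the proportion at the treatment assessment timepoint.

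**Conclusion.** The point holds as one of definition and labelling. As written, the exploratory haptoglobin endpoints measure detectability, count any value between the detection limit and the LLN as normalised, and leave the number of patients reaching the LLN without a planned summary. The size is unknown and may be zero. The direction in step 3 rests on the single assumption that the detection limit lies below the LLN. The primary and secondary analyses are unaffected, as is the Part B SAP, which treats haptoglobin only as a continuous variable (Part B SAP, Section 7.2.1).

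**What to change.** In Part A SAP Section 5.1.1, define haptoglobin normalisation as a value at or above the central-laboratory LLN, and apply it to the proportion at the treatment assessment timepoint, the proportion by visit and the time to first normalisation. Keep the present criterion as a separate result named *detectable haptoglobin*. In the same edit, state how results below the detection limit enter the Week 23, 25 and 26 mean, and how patients who already meet a criterion at baseline are handled. The latter is needed because no inclusion criterion in Protocol Section 5.1 concerns haptoglobin.

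If the Part A database has already been locked, relabel the outputs and add the LLN version as an identified additional analysis.

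The cost is small. Haptoglobin is already in the chemistry panel (Protocol Appendix A), so no new samples are needed; the work is one definition and a few table rows. The downside is that the exploratory proportion may be lower and the time longer.
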